7.2 Adverse Event Reporting

Unanticipated problems related to the research involving risks to subjects or others that occur during this study (including SAEs) will be reported to the IRB in accordance with CHOP IRB SOP 408: Unanticipated Problems Involving Risks to Subjects. AEs that do not meet prompt reporting requirements will be summarized in narrative or other format and submitted to the IRB at the time of continuing review (if continuing reviews are required) or will be tracked and documented internally by the study team but not submitted to the IRB (if continuing reviews are not required).

7.3 Definition of an Adverse Event

An adverse event is any untoward medical occurrence in a subject who has received an intervention (drug, biologic, or other intervention). The occurrence does not necessarily have to have a causal relationship with the treatment. An AE can therefore be any unfavorable or unintended sign (including an abnormal laboratory finding, for example), symptom, or disease temporally associated with the use of a medicinal product, whether or not considered related to the medicinal product.

All AEs (including serious AEs) will be noted in the study records and on the case report form with a full description including the nature, date and time of onset, determination of non-serious versus serious, intensity (mild, moderate, severe), duration, causality, and outcome of the event.

The severity of AEs will be graded according to the following scale:

Mild: Does not interfere in a significant manner with the patient's normal functioning level. It may be an annoyance. Prescription drugs are not ordinarily needed for relief of symptoms but may be given because of personality of the patient.

Moderate: Produces some impairment of functioning but is not hazardous to health. It is uncomfortable or an embarrassment. Treatment for symptoms may be needed.

Severe: Produces significant impairment of functioning or incapacitation and is a definite hazard to the patient's health. Treatment for symptom may be given and/or patient hospitalized.

Injection Site Reactions

The severity of injection site reactions will be graded according to the following scale (semi-colon indicates "or" within description of grade):

Mild: Pain that does not interfere with activity; mild discomfort to touch; <5 cm of erythema or induration that does not interfere with activity

Moderate: Pain that requires repeated use of non-narcotic pain reliever >24 hours or interferes with activity; discomfort with movement; 5.1 cm to 10 cm erythema or induration or induration that interferes with activity

Severe: Pain that requires any use of narcotic pain reliever or that prevents daily activity; significant discomfort at rest; >10 cm erythema or induration; prevents daily activity; requires emergency room visit or hospitalization; necrosis or exfoliative dermatitis

7.4 Causality

The investigator must provide causality assessment as to whether or not there is a reasonable possibility that the drug caused the AE, based on evidence or facts, his/her clinical judgment, and the following definitions. The causality assessment must be made based on the available information and can be updated as new information becomes available.

The following factors should be considered when assessing causality:

- Temporal relationship: time to onset versus time drug was administered
- Nature of the reactions: immediate versus long term
- Clinical and pathological features of the events
- Existing information about the drug and same class of drugs
- Concomitant medications
- Underlying and concurrent illnesses
- Response to dechallenge (drug discontinuation) or dose reduction
- Response to rechallenge (re-introduction of the drug) or dose increase, when applicable
- Patient's medical and social history

Causality to the study drug (including study drug administration):

- Related:
 - The AE follows a reasonable temporal sequence from study drug administration, and cannot be reasonably explained by the nature of the reaction, patient's clinical state (e.g., disease under study, concurrent diseases, concomitant medications), or other external factors.

Or

- The AE follows a reasonable temporal sequence from study drug administration, and is a known reaction to the drug under study or its class of drugs, or is predicted by known pharmacology.

• Not Related:

- The AE does not follow a reasonable sequence from study drug administration, or can be reasonably explained by the nature of the reaction, patient's clinical state (e.g., disease under study, concurrent diseases, and concomitant medications) or other external factors.

Causality to the study conduct (protocol-specified procedure):

- Related:

- The AE follows a reasonable temporal sequence from a protocol-specified procedure, and cannot be reasonably explained by the nature of the reaction, patient's clinical state (e.g., disease under study, concurrent diseases, concomitant medications), or other external factors.

- Not Related:

- The AE does not follow a reasonable sequence from a protocol-specified procedure, or can be reasonably explained by the nature of the reaction, patient's clinical state (e.g., disease under study, concurrent diseases, and concomitant medications) or other external factors.

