5.4.5 Safety Analysis

All AEs will be coded by system organ class and preferred term using MedDRA.

Treatment-emergent AEs (TEAEs) will be defined as any AEs, regardless of relationship to study drug, which occur during AE collection period of study drug or any event already present that worsens in either intensity or relationship to study drug following exposure to the dupilumab. If relationship information is missing, the TEAE will be considered drug related.

An overall summary of TEAEs will be provided showing the number and percentage of subjects in each treatment group with any TEAE, any potentially drug related TEAE, any severe TEAE, any serious TEAE, any TEAE leading to discontinuation, and any TEAE leading to death. The number of events will also be presented.

The number of AEs as well as the number and percentage of subjects who experienced at least one AE will be summarized by system organ class, preferred term, and time period. The incidence of the following events will be summarized:

- TEAEs: incidence, severity, and duration.
- Potentially drug related TEAEs
- Discontinuations due to TEAEs
- Physical examinations, and vital signs
- SAEs
- Potentially drug-related SAEs

In addition, TEAEs will be summarized by relationship to study drug and by severity. If a subject has more than one occurrence of the same TEAE with different severities or relationship to study drug, then the TEAE will be assigned to the highest severity category and/or most related relationship category. If the intensity or relationship is missing, then the 'worst case' will be assumed (i.e., severe for intensity and drug-related for relationship).

Time period of an AE will be determined based on the start time of the AE.

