7.5 Definition of a Serious Adverse Event (SAE)

An SAE is any adverse drug experience occurring at any dose that results in any of the following outcomes:

- death,
- a life-threatening event (at risk of death at the time of the event),
- requires inpatient hospitalization or prolongation of existing hospitalization,
- a persistent or significant disability/incapacity, or
- a congenital anomaly/birth defect in the offspring of a subject.

Important medical events that may not result in death, be life-threatening, or require hospitalization may be considered a serious adverse drug event when, based upon appropriate medical judgment, they may jeopardize the subject and may require medical or surgical intervention to prevent one of the outcomes listed in this definition.

A distinction should be drawn between serious and severe AEs. A severe AE is a major event of its type. A severe AE does not necessarily need to be considered serious. For example, nausea which persists for several hours may be considered severe nausea but would not be an SAE. On the other hand, a stroke that results in only a limited degree of disability may be considered a mild stroke but would be an SAE.

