7.5.1 Relationship of SAE to study drug or other intervention

The relationship of each SAE to the study intervention should be characterized using one of the following terms in accordance with CHOP IRB Guidelines: definitely, probably, possibly, unlikely, or unrelated.

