7.6 IRB/IEC Notification of SAEs and Other Unanticipated Problems

The Investigator will promptly notify the IRB of all on-site unanticipated, serious Adverse Events that are related to the research activity. Other unanticipated problems related to the research involving risk to subjects or others will also be reported promptly. Written reports will be filed using the eIRB system and in accordance with the timeline below. External SAEs that are both unexpected and related to the study intervention will be reported promptly after the investigator receives the report.

Type of Unanticipated Problem	Initial Notification (Phone, Email, Fax)	Written Report
Internal (on-site) SAEs Death or Life Threatening	24 hours	Within 2 calendar days
Internal (on-site) SAEs All other SAEs	7 days	Within 7 business days
Unanticipated Problems Related to Research	7 days	Within 7 business days
All other AEs	N/A	Brief Summary of important AEs may be reported at time of continuing review

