7.10 Regulatory and Ethical Considerations

7.10.1 Data and Safety Monitoring Plan

The principal investigator (PI) will monitor adverse events and other safety concerns during the study. As the drug is approved for this age group and has been studied in this indication, little new adverse events are expected. The main novel adverse event will be with food introduction while on dupilumab. The symptoms and side effects will be monitored at regular study visits for worsening EoE symptoms. In addition, the endoscopies at week 12 after the introduction will examine if active disease has returned and the food introduction will be adjusted.

The PI will ensure the accuracy, security, and validity of the data via oversight of data storage, integrity, and laboratory methodology including statistical analysis. The PI will provide oversight of study personnel to ensure the safety of enrolled subjects by enforcing the protections and safeguards outlined in the protocol.

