7.10.2.3 Risks from food introduction

The main risk from food introduction is exacerbation of Eosinophilic Esophagitis symptoms. Subjects will be monitored one week by phone for increasing symptoms and study visits for worsening symptoms by validated EoE questionnaires. In addition, the other risk is worsening esophageal histology and possible long-term fibrosis with untreated disease. Therefore, we monitor for worsening disease at 12 weeks after food introduction by upper endoscopy with biopsy.

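### Section 7.4 has no causality category for trigger-food introduction, so an EoE flare on food can be scored Not Related and no planned safety table isolates such events

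*Combined protocol and SAP*

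**What the plan says.** Section 7.10.1 states: "The main novel adverse event will be with food introduction while on dupilumab". Section 7.10.2.3 says what that event is: "The main risk from food introduction is exacerbation of Eosinophilic Esophagitis symptoms". Section 7.10.4 lists food introduction beside endoscopy and dupilumab as one of three sources of risk.

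Section 7.4 gives two causality axes, study drug and protocol-specified procedure. On each, an event is Not Related if its timing does not fit, or if it is reasonably explained by the nature of the reaction or by the patient's "clinical state (e.g., disease under study, concurrent diseases, and concomitant medications) or other external factors". The assessment also draws on the investigator's clinical judgment and a list of factors that includes timing.

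Section 5.4.5 counts TEAEs whatever their relationship to drug and summarises AEs by system organ class, preferred term and period. The only relationship it tabulates is to study drug. On timing it says: "Time period of an AE will be determined based on the start time of the AE". It does not define the periods.

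Section 7.5 begins "An SAE is any adverse drug experience occurring at any dose". Section 7.5.1 grades SAEs as "definitely, probably, possibly, unlikely, or unrelated", with no mapping to the two-level scale of 7.4. Section 7.6 says: "The Investigator will promptly notify the IRB of all on-site unanticipated, serious Adverse Events that are related to the research activity".

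**The concern.** The trial deliberately gives patients a food known to trigger their disease. The expected harm is therefore an exacerbation of that disease, and the plan accepts exactly that explanation as a reason to score an event Not Related. The usual exclusion for background disease does not suit a study whose intervention provokes the disease.

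At stake is the goal stated in the synopsis, that foods can be safely added while on dupilumab. Supporting it calls for a count of clinical events attributed to food among those who started food. The study is open label with a single arm, so no comparison group can supply that attribution, and the principal investigator monitors safety. If attribution and the date of worsening are not captured when the event occurs, they cannot be reliably reconstructed later.

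**Working it through.** The plan states no figure for this point, so the check is mainly a trace of two cases through its rules.

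**Case A: dysphagia or food impaction that begins after trigger food.**
1. *Drug axis, Related.* The first limb requires that the disease under study cannot reasonably explain the event, and EoE does explain it. The second limb covers known or predicted reactions to the drug, and a food flare is not one. Result: can be Not Related.
2. *Procedure axis, Related.* Suppose food introduction counts as a procedure, since Table 1 lists it. The same disease clause applies, and this axis has no limb for known or predicted reactions. Result: can be Not Related.
3. *Tables.* A procedure-related score would still appear in no specified table, because 5.4.5 summarises relationship to study drug only.
4. *Period.* The event starts after food and is dated after food, so the start-time rule does no harm here.

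**Case B: a symptom present before food that worsens on food.** For example, mild dysphagia begins in week 5 and becomes severe in week 20.
1. This can occur because the synopsis lets subjects start food with decreased symptoms, not absent ones.
2. Section 5.4.5 counts worsening as a TEAE relative to dupilumab exposure, not to food. It does not say whether worsening opens a new record.
3. If the original record is kept, its start is week 5, before food at week 13, and the event falls in the pre-food period. If a new record is opened, it falls after food. The plan permits either.

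**Scale, as illustration only.** The documents give no flare rate, so 10% to 50% is assumed.
- Subjects reaching food: 30 × 0.64 = 19.2, and with the two trial rates in 5.6, 30 × (67% + 59.5%)/2 = 18.98. Both reproduce the plan's 19.
- Let p be the assumed flare rate and q the assumed share of flares that continue an existing symptom under its original start date. Expected subjects with a flare = 19p. Expected number dated after food = 19p(1 − q).

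| p | 19p | After food, q = 25% | q = 50% | q = 75% | 19p as % of 30 |
|---|---|---|---|---|---|
| 10% | 1.9 | 1.4 | 1.0 | 0.5 | 6.3% |
| 20% | 3.8 | 2.9 | 1.9 | 1.0 | 12.7% |
| 30% | 5.7 | 4.3 | 2.9 | 1.4 | 19.0% |
| 50% | 9.5 | 7.1 | 4.8 | 2.4 | 31.7% |

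The last column applies if percentages use all 30 treated subjects, as a summary by treatment group in a single-arm trial suggests. A food-event rate is then diluted by 19/30 = 0.63.

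The timing rule lowers the after-food count but does not by itself remove it. The chance that no flare is dated after food is (1 − p(1 − q))^19. At p = 20% this is 0.8^19 = 1.4% with q = 0, and 0.9^19 = 13.5% with q = 50%.

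**The case against.** A reader might infer that the main novel risk could be reported as zero. The documents do not support that. TEAEs, severe and serious TEAEs, and AEs by period are tabulated without regard to causality, so a flare recorded as an AE is counted. Flares are also measured by the primary eosinophil endpoint, the two eosinophil-threshold endpoints and symptom scores by time point, and 5.2 lists endoscopy and biopsy as safety monitoring. A food flare missing from the drug-related rows is not concealment, since those rows ask about the drug and will hold drug reactions.

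A reader might also infer that sites must score a flare Not Related. Section 7.4 permits this but does not compel it: the test is reasonable explanation, judgment applies, and timing is a listed factor.

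Nor does the plan say that worsening is generally dated before food at its highest severity. Only a symptom already present and not re-entered is affected. The highest-severity rule concerns repeated occurrences in the relationship and severity summaries, and no severity-by-period table is specified.

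On IRB reporting, 7.3 and 7.5.1 refer to interventions other than drug, and 7.6 does not tie research activity to the 7.4 categories. The notification sentence also requires the event to be unanticipated, so an expected flare might not qualify whatever its causality score.

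All of this stands, and it limits the point. It does not supply what is missing. Biopsies and symptom scores do not attribute a clinical event between visits, such as a food impaction, to food. The symptom responder analysis in 5.4.3.6 compares end of treatment with baseline, so improvement on drug can offset a flare in mid-study.

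**Conclusion.** The point holds as a gap in attribution and presentation. The stated rules allow the harm most expected from the trial's own food intervention to be scored Not Related on both axes. No planned table isolates food-related events, and the by-period counts can understate worsening on food when the symptom was already present.

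Severity is moderate. The primary endpoint, sample size and primary conclusion are unaffected, and the events stay visible in the unfiltered counts. The verdict rests on the wording of 7.4 and 5.4.5, and on the assumption that sites may apply the disease clause literally and may keep one record for a worsening symptom. The number of events affected cannot be derived from the documents; the table above shows only what follows from assumed rates.

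**What to change.** 1. In 7.4, add a third assessment, causality to trigger-food introduction, in which explanation by EoE itself does not make the event Not Related. Add one eCRF field for it.
2. In 5.4.5, define the AE periods as pre-food and each food step. Record any worsening after a food step as a new event dated at the worsening.
3. In 5.4.5, tabulate TEAEs by food-relatedness, with subjects who started food as the denominator.
4. In 7.5 and 7.6, state that food introduction is a study intervention and a research activity.
5. Map the five terms in 7.5.1 to Related and Not Related.

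The cost is protocol wording, one eCRF field and one table, with no new procedure, visit or patient. The downside is that some flares will be reported as research-related.

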7.5 Definition of a Serious Adverse Event (SAE)

An SAE is any adverse drug experience occurring at any dose that results in any of the following outcomes:

- death,
- a life-threatening event (at risk of death at the time of the event),
- requires inpatient hospitalization or prolongation of existing hospitalization,
- a persistent or significant disability/incapacity, or
- a congenital anomaly/birth defect in the offspring of a subject.

Important medical events that may not result in death, be life-threatening, or require hospitalization may be considered a serious adverse drug event when, based upon appropriate medical judgment, they may jeopardize the subject and may require medical or surgical intervention to prevent one of the outcomes listed in this definition.

A distinction should be drawn between serious and severe AEs. A severe AE is a major event of its type. A severe AE does not necessarily need to be considered serious. For example, nausea which persists for several hours may be considered severe nausea but would not be an SAE. On the other hand, a stroke that results in only a limited degree of disability may be considered a mild stroke but would be an SAE.

7.5.1 Relationship of SAE to study drug or other intervention

The relationship of each SAE to the study intervention should be characterized using one of the following terms in accordance with CHOP IRB Guidelines: definitely, probably, possibly, unlikely, or unrelated.

7.6 IRB/IEC Notification of SAEs and Other Unanticipated Problems

The Investigator will promptly notify the IRB of all on-site unanticipated, serious Adverse Events that are related to the research activity. Other unanticipated problems related to the research involving risk to subjects or others will also be reported promptly. Written reports will be filed using the eIRB system and in accordance with the timeline below. External SAEs that are both unexpected and related to the study intervention will be reported promptly after the investigator receives the report.

Type of Unanticipated Problem	Initial Notification (Phone, Email, Fax)	Written Report
Internal (on-site) SAEs Death or Life Threatening	24 hours	Within 2 calendar days
Internal (on-site) SAEs All other SAEs	7 days	Within 7 business days
Unanticipated Problems Related to Research	7 days	Within 7 business days
All other AEs	N/A	Brief Summary of important AEs may be reported at time of continuing review

7.6.1 Follow-up report

If an SAE has not resolved at the time of the initial report and new information arises that changes the investigator's assessment of the event, a follow-up report including all relevant new or reassessed information (e.g., concomitant medication, medical history) should be submitted to the IRB. The investigator is responsible for ensuring that all SAE are followed until either resolved or stable.

7.7 STUDY ADMINISTRATION

7.7.1 Treatment Assignment Methods

7.7.2 Randomization

Not applicable, all patients are receiving active therapy

7.7.3 Blinding

Not applicable, all patients are receiving active therapy

7.8 Data Collection and Management

An eCRF will be used for the current study, and a data management plan will be prepared by the BDMC (Biostatistics and Data management Core) at CHOP managed by Westat. The data will be entered in REDCap (prepared by Westat).

Previous and concomitant medications will be coded using the latest available World Health Organization (WHO) Drug Reference Dictionary. Coexistent diseases and AEs will be coded using Medical Dictionary for Regulatory Activities (MedDRA).

When the database has been declared to be complete and accurate, the database will be locked. Any changes to the database after that time can only be made by written agreement between the investigator and the Westat BioStat unit.

7.9 Confidentiality

No identifiable data will be used for future study without first obtaining IRB approval or determination of exemption. The investigator will obtain a data use agreement between the provider (the PI) of the data and any recipient researchers (including others at CHOP) before sharing a limited dataset (PHI limited to dates and zip codes).

